9.6.3 Concomitant medication

Concomitant medication will be coded using the WHO drug dictionary (Version September 2021). Concomitant medication will be listed.

9.6.4 Clinical laboratory parameters

Clinical laboratory data are collected at screening only and, with the exception of those reported in the demographics, will not be presented.

9.6.5 Vital signs

Vital signs data will be listed for individual participants.

9.6.6 Electrocardiogram (ECG)

ECGs will be performed for screening and will not be presented.

9.6.7 Perceived Exertion during Exercise

The **CC** scale is a well-validated tool⁴ to assess perceived physical effort during exercise; it is presented as a scale **CC** anchored by verbal descriptors. This scale describes different efforts: is no exertion at all and it the maximal exertion or hardest possible effort. Participants will be asked to point to a number that best describes their feelings of the exercise at that moment.

During screening, prospective study participants will have their exercise capacity assessed during a progressive treadmill exercise test until volitional fatigue, as part of the study eligibility. As part of this assessment, the RPE score will be collected every 2 minutes. The data will be listed for those participants who are then enrolled into the study.

During each exercise period, participants will record their perceived physical effort using the RPE score the last 2 minutes of each exercise interval over the 1-hour exercise period. The data will be listed and summarized by assessment day (Visit 2-Humalog) and in-house visit (Visit 3,4,5,6) and by treatment (Lyumjev vs Humalog for the corresponding basal rate reduction).

9.6.8 Other assessments

All other safety assessments not detailed in this section will be listed but not summarized or statistically analyzed.

9.6.9 Safety and Tolerability Statistical Methodology

No inferential statistical analyses are planned.

10. INTERIM ANALYSES

No interim statistical analyses are planned.

11. CHANGES FROM THE PROTOCOL SPECIFIED STATISTICAL ANALYSES

There were no changes from the protocol specified statistical analyses.

13. DATA PRESENTATION

13.1 Derived Parameters

Individual derived parameters (e.g. PK parameters) and appropriate summary statistics will be reported to three significant figures. Observed concentration data, e.g. C_{max} , should be reported as received. Observed time data, e.g. t_{max} , should be reported as received. N and percentage values should be reported as whole numbers. Median values should be treated as an observed parameter and reported to the same number of decimal places as minimum and maximum values.

13.2 Missing Data

Missing data will not be displayed in listings.

13.3 Insufficient Data for Presentation

Some of the TFLs may not have sufficient numbers of participants or data for presentation. If this occurs, the blank TFL shell will be presented with a message printed in the center of the table, such as, "No serious adverse events occurred for this study."

14. **APPENDICES**

Status and Version	Date of Change	Summary/Reason for Changes
Final Version 1.0	NA	NA; the first version.
Final Version 2.0	31MAR2023	Update to primary analysis

NA = not applicable

Appendix 2: Supplementary material

To find the CIs associated with the treatment ratio μ_T/μ_R , Fieller's theorem will be used, the equations to calculate the lower and upper interval values as follows:

$$L_{1-\alpha/2} = \frac{1}{1-G} \left\{ \left(\frac{\overline{Y_T}}{\overline{Y_R}} - G \frac{S_{RR}}{S_{RR}^2} \right) - \left[t(\alpha/2, n_1 + n_2 - 2) \sqrt{\omega S_{RR}^2} / \overline{Y_R} G^* \right] \right\},\$$
$$U_{1-\alpha/2} = \frac{1}{1-G} \left\{ \left(\frac{\overline{Y_T}}{\overline{Y_R}} - G \frac{S_{RR}}{S_{RR}^2} \right) + \left[t(\alpha/2, n_1 + n_2 - 2) \sqrt{\omega S_{RR}^2} / \overline{Y_R} G^* \right] \right\},\$$

where

$$G = \left[t \left(\frac{\alpha}{2}, n_1 + n_2 - 2 \right) \right]^2 \left(\frac{\omega S_{RR}^2}{Y_R^2} \right),$$

$$G^* = \left(\frac{\overline{Y_T}}{\overline{Y_R}} \right)^2 + \frac{S_{TT}^2}{S_{RR}^2} (1 - G) + \frac{S_{TR}}{S_{RR}^2} \left(\frac{G S_{TR}}{S_{RR}^2} - 2 \frac{\overline{Y_T}}{\overline{Y_R}} \right),$$

$$\omega = \frac{1}{4} \left(\frac{1}{n_1} + \frac{1}{n_2} \right),$$

 $\overline{Y_R}$ is the LSM estimate of the reference mean, $\overline{Y_T}$ is the LSM estimate of the treatment mean, and t(a,q) is the value of the student's t-distribution pdf at the ath percentile with q degrees of freedom.

Signature Page for VV-CLIN-094317 v1.0

Approval	PPD
	31-Mar-2023 16:22:24 GMT+0000
Approval	PPD
	03-Apr-2023 09:21:09 GMT+0000
Approval	PPD
	05-Apr-2023 03:13:35 GMT+0000

Signature Page for VV-CLIN-094317 v1.0

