9.3.2 Pharmacokinetic Statistical Methodology

The modified full analysis population will be used for these analyses. The PK parameters for the MMTT and during exercise will be analyzed separately.

During the MMTT

Log-transformed PK parameters AUCs, and C_{max} from insulin lispro during the MMTT will be statistically analyzed using a mixed-effect model. The model will include treatment (Lyumjev or

Humalog) and period as fixed effects, and participant as a random effect. The least squares (LS) means will be back-transformed to produce the treatment geometric LS means, ratio of geometric LS means of Lyumjev to Humalog, and corresponding 90% CIs, as well as the p-value, will be reported.

Example of the SAS code is as follows:

```
proc mixed data=xxx;
  class treat period usubjid;
  model logPK = treat period /residual ddfm=kr;
  random usubjid;
  lsmeans treat / cl pdiff alpha=0.1;
  estimate `Lyumjev vs Humalog' treat 1 -1/ CL alpha=0.1;
  ods output lsmeans=lsm diffs=estims;
run;
```

The same analysis without log transformation will be performed on the PK time parameters (early 50% t_{max} , late 50% t_{max} , and t_{max}) during the MMTT. The treatment LS means, treatment difference in LS means between Lyumjev and Humalog, and corresponding 90% CIs, as well as the 2-sided p-value, will be reported. The treatment ratios and 90% CIs for the ratios will be calculated using the Fieller's theorem³, see Appendix 2 for further details on this calculation.

Statistical significance will be achieved when the p-value for a test is less than 0.10.

During exercise

A mixed-effects model without log transformation that includes treatment (Lyumjev with 50% basal reduction, Lyumjev with 100% basal reduction, Humalog with 50% basal reduction, and Humalog with 100% basal reduction), sequence, and period as fixed effects and participant-within-sequence as a random effect may be used for the exploratory PK endpoints during the exercise period. LS means, treatment differences in LS means, and the corresponding 90% CIs for the treatment differences will be estimated from the model. The p-value on the difference between LS means will be used to determine statistical significance. The treatment ratios and 90% CIs for the ratios will be calculated using the Fieller's theorem (Chow and Liu 2009).

Additionally, exploratory analysis may be conducted if deemed necessary upon review of the data.

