9.4.2 Pharmacodynamic Statistical Methodology

Primary glucodynamic endpoint

Changes in PG from the start to end of exercise will be statistically analyzed using a mixed– effect model. The model will include treatment (Lyumjev with 50% basal reduction, Lyumjev with 100% basal reduction, Humalog with 50% basal reduction, and Humalog with 100% basal reduction), sequence, period, timepoint, treatment-by-timepoint interaction as fixed effects, and participant-within-sequence as a random effect. Baseline (0 min timepoint) will be included as a covariate. The LS means, difference LS means between Lyumjev and Humalog for corresponding basal rate reduction, and corresponding 90% CIs, as well as the p-value, will be reported.

The p-value on the difference between LS means will be used to determine statistical significance.

Secondary glucodynamic endpoints

For the derived glucodynamic parameters iAUCs Δ PGmax, Δ PG1h, and Δ PG2h, a statistical analysis will be performed during exercise with a basal reduction, and after the MMTT independently. The modified full analysis population will be used for this analysis.

The parameters iAUCs during the MMTT and AUCs during exercise will be log-transformed before the statistical analysis. If negative values occur, the analysis will be performed on untransformed parameters. A mixed effects model will be used for this analysis. The model will include treatment (Lyumjev with 50% basal reduction, Lyumjev with 100% basal reduction, Humalog with 50% basal reduction, and Humalog with 100% basal reduction), sequence, and period as fixed effects, and participant-within-sequence will be included as a random effect. The LS means will be back-transformed to produce geometric means. The treatment geometric LS mean of each treatment, ratio of geometric means between Lyumjev and Humalog for corresponding basal rate reduction, and corresponding 90% CIs will be reported. The p-value will also be reported for the ratios. If the analysis is done on the untransformed parameters, the treatment LS means, difference in LS means between Lyumjev and Humalog for corresponding

basal rate reduction, and corresponding 90% CIs, as well as the p-value, will instead be reported. The treatment ratios and 90% CIs for the ratios will be calculated using the Fieller's theorem.

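### The Fieller limits printed in SAP Appendix 2 do not solve Fieller's equation, so the supportive 90% ratio intervals can come out too wide or too narrow

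*SAP*

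**What the plan says.** Appendix 2 of the SAP is the only place where the ratio intervals are written out. It introduces them with "Fieller's theorem will be used, the equations to calculate the lower and upper interval values as follows" and then prints a lower limit, an upper limit and the auxiliary quantities `G`, `G*` and `ω`. As printed:

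- **Centre:** `Y_T/Y_R − G·S_RR/S_RR^2`, the same in both limits.
- **Half-width:** `t·sqrt(ω·S_RR^2)/Y_R · G*`, with no root over `G*`. `G*` itself is defined without a root.
- **Scale:** `ω = (1/4)(1/n1 + 1/n2)`, with `n1 + n2 − 2` degrees of freedom.
- **t:** the closing sentence says that "t(a,q) is the value of the student's t-distribution pdf at the ath percentile with q degrees of freedom".

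The S terms, `n1` and `n2` are not defined.

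SAP 9.3.2 sends the reader here for the MMTT lispro time parameters ("see Appendix 2 for further details on this calculation") and also plans Fieller ratios for exercise PK. SAP 9.4.2 plans them for AUCs and iAUCs analysed untransformed ("The treatment ratios and 90% CIs for the ratios will be calculated using the Fieller's theorem"), for the rate of change in plasma glucose and for the exploratory glucodynamic time parameters.

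Significance is decided elsewhere. In 9.3.2, "Statistical significance will be achieved when the p-value for a test is less than 0.10", and the p-value is the one for the difference in LS means.

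**The concern.** A Fieller interval at the 90% level excludes 1 exactly when the two-sided test of the difference has p below 0.10, provided both use the same variance and degrees of freedom and the interval is finite (`G < 1`). SAP 9.3.2 reports the difference, its p-value and the ratio interval together for the same parameter. If the ratio limits do not solve Fieller's equation, that agreement is lost. A table could show a ratio interval that excludes 1 beside p above 0.10, or the reverse, and the stated 90% level would not hold.

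**Working it through.** **Inputs.** From the SAP: the 90% level, the equations and t definition in Appendix 2, and 28 completers (section 7). Assumed, because the documents do not give them: a 14/14 split, so that `ω = (1/4)(1/14 + 1/14) = 1/28` with 26 df (the setting the formula is written for); CV 40%; Lyumjev-Humalog correlation from 0 to 0.9.

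**1. Solve the equation.** The limits for `ρ = μ_T/μ_R` satisfy

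`(Y_T − ρ·Y_R)^2 = t^2·ω·(S_TT^2 − 2ρ·S_TR + ρ^2·S_RR^2)`.

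Divide by `Y_R^2` and put `G = t^2·ω·S_RR^2/Y_R^2`:

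`(1 − G)·ρ^2 − 2ρ·(Y_T/Y_R − G·S_TR/S_RR^2) + (Y_T/Y_R)^2 − G·S_TT^2/S_RR^2 = 0`.

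The quarter-discriminant equals `G` times the `G*` printed in the SAP. The roots are therefore

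`{(Y_T/Y_R − G·S_TR/S_RR^2) ± sqrt(G)·sqrt(G*)}/(1 − G)`, where `sqrt(G) = t·sqrt(ω·S_RR^2)/Y_R`.

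The printed `G*` is right, but it belongs under a root. The centre needs the covariance `S_TR`.

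**2. The t value.** With `a = 0.05` and 26 df, the density at the 5th percentile is 0.094. The multiplier needed is the upper 5% quantile, 1.706. (The 5th percentile itself is −1.706, which would swap the two limits, so the definition should say upper.)

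**3. Example.** Means 60 and 60, SD 24, correlation 0.8, `S_RR/S_RR^2` read as 1.

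- `G = 1.706^2 × (576/28)/3600 = 0.0166`; `sqrt(G) = 0.129`
- `G* = 1 + 0.9834 + 0.8 × (0.8 × 0.0166 − 2) = 0.394`
- Correct: `(1 − 0.0133 ± 0.129 × sqrt(0.394))/0.9834`, giving 0.921 to 1.086
- Printed, with the correct quantile: `(1 − 0.0166 ± 0.129 × 0.394)/0.9834`, giving 0.948 to 1.052

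The printed interval is `0.104/0.165 = 63%` of the correct width. At correlation 0, `G* = 1 + 0.9834 = 1.983`, and the printed half-width is `sqrt(1.983) = 1.41` times the correct one. The error runs both ways.

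**4. Coverage.** At ratio 1 with equal variances, `G*` is close to `2 − 2r`, so the crossover lies near `r = 0.5`. Simulated non-coverage, nominal 10%, correct quantile, root and subscript as printed:

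| Correlation | Correct formula | Printed formula |
|---|---|---|
| 0 | about 10% | 4% |
| 0.5 | about 10% | 11% |
| 0.7 | about 10% | 21% |
| 0.8 | about 10% | 30% |
| 0.9 | about 10% | 45% |

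The corrected interval agreed with p < 0.10 for the difference in every run when both used the same variance and df. The printed interval disagreed in 11%, 20% and 35% of runs at correlations 0.7, 0.8 and 0.9.

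**5. Each defect alone.** Across true ratios 0.70 to 1.25, CV 0.3 and 0.6, and correlations 0.2 to 0.9:

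- Missing root: 2% to 60% non-coverage.
- Wrong subscript, read as 1: 10% to 12%.
- Density used literally for t: 92% to 93%.

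**The case against.** **The equations may be misread.** The text used here was transcribed from a PDF, and a lost radical or a T read as R is a plausible slip. This stands as a caveat on the root and the subscript: both need a look at the source page. Two things weigh against a misread subscript: `S_RR` appears in both limits, and `S_TR` is read correctly inside `G*`. The density definition is ordinary prose and does not depend on the transcription.

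**Nobody would program a density.** Probably true. The notation `t(α/2, n1 + n2 − 2)`, the named theorem and the cited textbook all point to a quantile. The 92% figure shows what the sentence says, not what is likely to be run. The realistic risk is the missing root.

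**The subscript hardly matters.** Correct if `S_RR/S_RR^2` is read as 1: in the example it moves the centre by about `0.0166 × 0.2/0.9834 = 0.003`. The limits would depend on the measurement unit only if `S_RR` were an SD, which the SAP does not say.

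**The size rests on assumptions.** It does. The documents give neither CV nor correlation. At ratio 1, coverage is conservative at correlation 0 and close to nominal at 0.5.

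**The ratio intervals decide nothing.** This also stands. A reader might infer that the trial's false-positive rate is inflated well above 10%. The documents do not support that: significance rests on the p-value for the difference, no equivalence bounds are set for the ratios, and the primary analysis in 9.4.2 reports differences without a Fieller ratio. Some uses are conditional as well: untransformed AUCs arise only if negative values occur, and the exercise PK model is optional.

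**Correcting the symbols alone would not guarantee agreement with the p-value.** Correct. The example code in 9.3.2 uses Kenward-Roger df from a mixed model, while Appendix 2 uses a two-group `ω` and `n1 + n2 − 2`, in a trial with four sequences. The fix has to cover this.

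**Conclusion.** The point holds in limited form. The formula in Appendix 2 does not deliver the method it names. The t definition is wrong in plain text. The missing root and the subscript are wrong as transcribed, subject to confirmation on the source page. With the correct quantile, the missing root drives the result: non-coverage runs from about 4% to 45% over correlations 0 to 0.9, given a true ratio of 1, CV 40% and 14 participants in each of two groups. It would be wrong to say that the intervals are always too narrow.

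The effect is confined to supportive ratio intervals: MMTT PK time parameters, exercise PK, rate of change in plasma glucose, glucodynamic time parameters, and AUCs or iAUCs analysed untransformed. The primary endpoint and the tests of significance are untouched.

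**What to change.** Check the equations against the source page, then amend Appendix 2:

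1. Use `sqrt(G*)` in the half-width of both limits.
2. Use `S_TR/S_RR^2` in the centre of both limits.
3. Define `t(a,q)` as the upper a-th quantile of Student's t with q degrees of freedom.
4. Define the S terms, and take the variances and covariance of the LS means, and the df of the reported difference, from the fitted mixed model in place of `ω` and `n1 + n2 − 2`.
5. Add a programming check that the ratio interval excludes 1 exactly when the reported p-value for the difference is below 0.10. State that it applies where `G < 1`; otherwise Fieller's set is not a finite interval.

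The cost is a short revision of one appendix and one validation step. No new data are needed. Any ratio intervals already produced with the printed formula should be rerun; some will widen and some will narrow.
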